12.0 BLOOD DONATION

Subjects should not donate blood while participating in this study or for at least 90 days following the last infusion of atezolizumab or until 28 days after the last dose of Vigil, whichever occurs longest.

13.0 OCCUPATIONAL SAFETY

Study medications are not expected to pose significant occupational safety risks to investigational staff under normal conditions of use and administration. However, precautions should be taken to avoid direct contact with study medication. Biosafety Level 1 practices shall be employed with this study medication. Reference the Pharmacy Reference Manual.

14.0 ADVERSE EVENTS

Adverse Event and Serious Adverse Event Definitions

Adverse Event

An AE is any untoward medical occurrence in a patient or clinical investigation subject administered a pharmaceutical product and that does not necessarily have a causal relationship with this treatment. An AE can therefore be any unfavorable and unintended sign (including a clinically significant abnormal laboratory finding), symptom, or disease temporally associated with the use of a medicinal (investigational) product, whether or not related to the medicinal (investigational) product.

Serious Adverse Event

An AE (experience) or reaction occurring at any dose should be classified as a serious adverse event (SAE) if any of the following occur:

- Initial or prolonged hospitalization
- A life-threatening condition (i.e. an event in which the patient was at risk of death at the time of the event; it does not refer to an event which hypothetically might have caused death if it was more severe)
- Significant disability/incapacity (i.e. the AE resulted in a substantial disruption of the subject's ability to carry out normal life functions)
- Congenital anomaly/birth defect
- It does not meet any of the above serious criteria, but may jeopardize the subject or may require surgical or medical intervention to prevent one of the outcomes listed above.
- Death

Definition of Adverse Events of Special Interest (AESI)

An adverse event of special interest (AESI) is one of scientific and medical interest specific to understanding of the atezolizumab and may require close monitoring and rapid communication by the investigator to the sponsor. An AESI may be serious or non-serious. The rapid reporting of AESIs allows ongoing surveillance of these events in order to characterize and understand them in association with the use of this investigational product.

AESIs for atezolizumab include but are not limited to events with a potential inflammatory or immune-related mechanism and which may require more frequent monitoring and/or interventions such as steroids, immunosuppressants and/or hormone replacement therapy. These AESIs are being closely monitored in clinical studies with atezolizumab monotherapy and combination therapy. An immune-related adverse event (irAE) is defined as an adverse event that is associated with drug exposure and is consistent with an immune-related mechanism of action and where there is no clear alternate etiology. Serologic, immunologic, and histologic (biopsy) data, as appropriate, should be used to exclude alternate etiologies and support an irAE diagnosis. Appropriate efforts should be made to rule out neoplastic, infectious, metabolic, toxin, or other etiologic causes of the irAE.

If the Investigator has any questions in regards to an adverse event (AE) being an irAE, the Investigator should promptly contact the Medical Monitor.

AESIs for this study include the following:

- Cases of potential drug-induced liver injury that include an elevated ALT or AST in combination with either an elevated bilirubin or clinical jaundice, as defined by Hy's Law and based on the following observations:
 - Treatment-emergent ALT or AST > $3 \times$ baseline value in combination with total bilirubin > $2 \times$ ULN (of which $\ge 35\%$ is direct bilirubin)

- \circ Treatment-emergent ALT or AST > 3 \times baseline value in combination with clinical jaundice
- Suspected transmission of an infectious agent by the study treatment, as defined below

Any organism, virus, or infectious particle (e.g., prion protein transmitting transmissible spongiform encephalopathy), pathogenic or non-pathogenic, is considered an infectious agent. A transmission of an infectious agent may be suspected from clinical symptoms or laboratory findings that indicate an infection in a patient exposed to a medicinal product. This term applies only when a contamination of study treatment is suspected.

- Pneumonitis
- Colitis
- Endocrinopathies: diabetes mellitus, pancreatitis, adrenal insufficiency, hyperthyroidism, and hypophysitis
- Hepatitis, including AST or ALT > 10 × ULN
- Systemic lupus erythematosus
- Neurological disorders: Guillain-Barré syndrome, myasthenic syndrome or myasthenia gravis, and meningoencephalitis
- Events suggestive of hypersensitivity, infusion-related reactions, cytokine release syndrome, influenza-like illness, systemic inflammatory response syndrome, and systemic immune activation
- Nephritis
- Ocular toxicities (e.g., uveitis, retinitis)
- Myositis
- Myopathies, including rhabdomyolysis
- Grade \geq 2 cardiac disorders (e.g., atrial fibrillation, myocarditis, pericarditis)

Criteria for Hy's Law (FDA Guidance 2009)

- The drug causes hepatocellular injury, generally shown by a higher incidence of 3-fold or greater elevations above the ULN of ALT or AST than the (non-hepatotoxic) control drug
- Among trial subjects showing such aminotransferase elevations, often with aminotransferases much greater than 3 x ULN, one or more also show elevation of serum total bilirubin to >2 x ULN, without initial findings of cholestasis (elevated serum alkaline phosphatase)
- No other reason can be found to explain the combination of increased aminotransferases and total bilirubin, such as viral hepatitis A, B, or C; pre-existing or acute liver disease; or another drug capable of causing the observed injury.

Unexpected Adverse Event

An unexpected event is any AE that is not identified in nature, severity or frequency in the Clinical Investigator's brochure or the drug package insert.

Grading Adverse Events

Adverse events (AEs) will be recorded throughout the trial. Toxicities and AEs will be graded and reported using the Common Toxicity Criteria for Adverse Events (CTCAE) Version 4.03 as linked in Appendix D.

Adverse events will be summarized using the MedDRA coding system or higher. The NCI-CTCAE will be used for AE grading. All AEs, regardless of severity, will be followed by the Treating Physician until resolution is satisfactory.

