6.2.2 Dose Reduction / Escalation

Dose reduction or dose increase is not allowed for Vigil or atezolizumab.

Dose Holding Criteria

Both atezolizumab and Vigil should be held for any of the following AEs. Cycles held for toxicity should be made up (that cycle number is delayed rather than skipped). Atezolizumab and Vigil held may be resumed in patients whose AEs recover to Grade 0-1, with the exception of rash, which should recover to Grade 2 or better.

- Grade 2 pneumonitis
- Aspartate aminotransferase (AST) or alanine aminotransferase (ALT) greater than 3 and up to 5 times upper limit of normal (ULN) or total bilirubin greater than 1.5 and up to 3 times ULN
- Grade 2 or 3 diarrhea or colitis
- Symptomatic hypophysitis, adrenal insufficiency, hypothyroidism, hyperthyroidism, or Grade 3 or 4 hyperglycemia
- Grade 2 ocular inflammatory toxicity
- Grade 2 or 3 pancreatitis, or Grade 3 or 4 increases in amylase or lipase levels (greater than 2.0 times ULN)
- Grade 3 or 4 infection
- Grade 2 infusion-related reactions
- Grade 3 rash
- Grade 2 nephritis

Based on the mechanism of action of atezolizumab leading to T-cell activation and proliferation, there is the possibility of observing immune related Adverse Events (irAEs) during the conduct of this study. Potential irAEs include immune related colitis, pneumonitis, hepatitis, and endocrinopathies. Subjects should be monitored for signs and symptoms of irAEs. Subjects should be monitored for signs and symptoms of irAEs. In the absence of an alternate etiology (e.g., infection or PD) signs or symptoms of colitis, pneumonitis, hepatitis, and endocrinopathy should be considered to be immune-related.

Study Regimen Delay

- Cycles held for toxicity should be made up and not deleted.
- Dosing of atezolizumab and Vigil may be restarted when toxicity is ≤ Grade 1 severity with the exception of rash which may be ≤ Grade 2.
- In case of immune related adverse events, treatment with atezolizumab and Vigil may be delayed for up to 15 weeks (12 weeks for steroid therapy plus 3 weeks for gradual steroid tapering to a dose of ≤ 10 mg/day of prednisone.
- Subjects who delay treatment for more than 15 weeks due to toxicities will be considered off study treatment (see Section 6.3 Withdrawal).

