- Treatment delay not related to toxic events (including subjects unable to adhere to dose schedule) may not extend for more than three days unless due to symptoms related to disease or infection in which case up to a 4-week delay is allowed.
- If ≥ one 2-week delay due to disease or infection occurs, subject status must be reviewed by sponsor.

Atezolizumab should be permanently discontinued for any of the following AEs:

- Any life-threatening or Grade 4 AE
- Grade 3 or 4 pneumonitis
- Aspartate aminotransferase (AST) or alanine aminotransferase (ALT) >5 times upper limit of normal or total bilirubin >3 times upper limit of normal
- Diarrhea with abdominal pain, fever, ileus, or peritoneal signs; increase in stool frequency (Grade 4) stool incontinence, need for intravenous hydration for more than 24 hours, gastrointestinal hemorrhage, and gastrointestinal perforation
- Grade 4 hypophysitis
- Myasthenic syndrome/myasthenia gravis, Guillain-Barré or meningoencephalitis (all grades)
- Grade 3 or 4 ocular inflammatory toxicity
- Grade 4 or any grade of recurrent pancreatitis
- Grade 3 or 4 infusion-related reactions
- Grade 4 rash
- Grade 3 or 4 nephritis
- Myocarditis (all grades)

For combination treatment, the occurrence of a Grade 3 or 4 toxicity attributed to Vigil will result in the cessation of Vigil dosing and continuation of single agent atezolizumab only.

Please reference https://www.gene.com/download/pdf/tecentrig_prescribing.pdf for full prescribing information regarding atezolizumab.

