APPENDIX C: ATEZOLIZUMAB EXPANSION SCHEDULE OF ASSESSMENTS

1 cycle = 3 weeks	Each Cycle	EOT (30 days) ¹	Response Follow- Up (quarterly) ²	Survival (3 years) ³
Physical Exam		Х		
Symptom-Directed Physical Exam ⁴	Х			
Performance Status (ECOG)	Х	Х		
Vital Signs (including weight)	X ⁵	Х		
Toxicity (AESI/SAEs)	Х	Х		
Concomitant Medications	Х	Х	X ⁶	X ⁷
Radiological Tumor Assessment ⁸	X ⁹	X ¹⁰	X	
Triplicate ECG (recommended)	Recommende checkpoin	ed per use with t inhibitors ¹¹		
CBC with differential	Х	Х		
Serum Chemistry ¹²	Х	Х		
TSH (recommended)	Recommende checkpoin	ed per use with t inhibitors ¹³		
Immune Function Analysis ¹⁴	Х	Х		
Atezolizumab Administration ¹⁵	Х			
CA-125 ¹⁶	Х	Х	X	X
Tumor Biopsy ¹⁷	Х	X		
Phone Contact				X

² Subjects that discontinue study treatment before disease progression will have radiological assessment of disease quarterly until disease progression.

¹ End of Treatment visit will occur 30 days (+ 5 days) after the last treatment or prior to commencement of subsequent treatment.

³ Assessment performed annually after disease progression.

⁴ Symptom-Directed Physical Exam performed by a medical provider.

⁵ Vítal signs (heart rate, respiratory rate, blood pressure, temperature, and O₂ saturation) should be obtained within 60 minutes prior to atezolizumab infusion.

⁶ Collect any post study therapies taken after participation in the study.

⁷ Collect any post study therapies taken after participation in the study.

⁸ Radiological Tumor Assessment to include chest, abdomen, and pelvis. Assessment will be done per RECIST criteria for measurable disease.

⁹Radiological Tumor Assessment will be performed every third cycle.

¹⁰ Radiological Tumor Assessment performed at End of TX if not done within the previous 45 days.

¹¹Due to potential risk of myocarditis associated with atezolizumab use, it is recommended that cardiac function be monitored prior to and periodically during treatment with atezolizumab. Triplicate ECGs performed periodically during treatment with atezolizumab may help identify potential cardiac events; however, Institutional standard practice for monitoring cardiac function during use of checkpoint inhibitors should be used throughout treatment with atezolizumab.

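### The AESI list in 14.0 does not agree with the action rules in 6.2.2, so 24-hour reporting of some drug-stopping events is ambiguous; separately, Appendix C conflicts with 14.5 on AE collection in Part 3

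*Combined protocol and SAP*

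**What the plan says.** **AESI definition and list (14.0).** A general paragraph describes AESIs, in open-ended terms, as events with a possible inflammatory or immune mechanism that may need closer monitoring, steroids, immunosuppressants or hormone replacement. A list for this study follows. Its endocrine item is "Endocrinopathies: diabetes mellitus, pancreatitis, adrenal insufficiency, hyperthyroidism, and hypophysitis". Its liver item is "Hepatitis, including AST or ALT > 10 × ULN", alongside a separate Hy's Law-type item (ALT or AST above 3 × baseline with total bilirubin above 2 × ULN or with jaundice). Its cardiac item starts at Grade 2: "cardiac disorders (e.g., atrial fibrillation, myocarditis, pericarditis". No skin event is named.

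**Action rules (6.2.2).** The hold list includes "Symptomatic hypophysitis, adrenal insufficiency, hypothyroidism, hyperthyroidism, or Grade 3 or 4 hyperglycemia" and Grade 3 rash. The permanent-discontinuation list for atezolizumab includes "Myocarditis (all grades", Grade 4 rash, and "Aspartate aminotransferase (AST) or alanine aminotransferase (ALT) >5 times upper limit of normal or total bilirubin >3 times upper limit of normal".

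**Reporting and recording.** Section 14.6 applies the 24-hour rule to SAEs and AESIs. Section 5.6 asks that the Study Physician be told of ongoing AEs that may delay or end treatment, with no time limit. Section 14.5 requires all AEs to be recorded during study treatment and for up to 30 days afterwards (ending earlier if another therapy starts), and 14.0 says AEs are recorded throughout the trial. The Appendix B toxicity row covers adverse events generally. The Appendix C row, for Part 3, reads "Toxicity (AESI/SAEs".

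**The concern.** Safety and tolerability of the combination are the primary objective, and 14.0 gives rapid communication and ongoing surveillance as the reason for having AESIs. One would therefore expect an event serious enough to end a study drug under 6.2.2 to be clearly inside the rapid-reporting system. Several are not clearly inside it, and two sites could classify the same non-serious event differently.

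Classification also affects the results. AESIs are a component of the safety evaluation in 16.1. If Part 3 staff work from the Appendix C schedule, AESI status would in practice decide whether a non-serious event is entered at all. Section 16.1 summarizes treatment-emergent AEs by grade, dose and tumor type but not by study part. Thinner collection late in treatment could then be read as better tolerability at long exposure.

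**Working it through.** No calculation in the plan bears on this point, so the check sets the sections side by side.

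**Step 1: the four event types.**

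| Event | Action in 6.2.2 | Study list in 14.0 | Not clearly covered |
|---|---|---|---|
| Myocarditis | Permanent discontinuation, any grade | Cardiac disorders from Grade 2, myocarditis given as an example | Grade 1 |
| AST/ALT | Hold above 3 and up to 5 × ULN; permanent discontinuation above 5 × ULN | Hepatitis, including above 10 × ULN; Hy's Law-type combination | Above 5 and up to 10 × ULN, if not judged hepatitis and without raised bilirubin or jaundice |
| Hypothyroidism | Hold if symptomatic | Not named (hyperthyroidism is) | Symptomatic hypothyroidism |
| Rash | Grade 3 hold; Grade 4 permanent discontinuation | No skin item | Both grades, unless an SAE |

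The only stand-alone transaminase value in the list is 10/5 = 2 times the discontinuation value.

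**Step 2: all items in 6.2.2.**

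- Hold items (10). Four are fully named as AESIs: pneumonitis, ocular toxicity, infusion reactions and nephritis. Four are partly named: liver tests, diarrhea or colitis, the endocrine group, and pancreatitis with amylase or lipase rises. Two are not named: rash and Grade 3–4 infection, the latter not an immune event as such. So 4 + 2 = 6 of 10 are not fully named.
- Permanent-discontinuation items (12). Seven are fully named: pneumonitis, hypophysitis, the neurological group, ocular toxicity, pancreatitis, infusion reactions and nephritis. Five have a gap: a non-serious Grade 4 AE, liver tests, diarrhea, Grade 4 rash and Grade 1 myocarditis.

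**Step 3: does the general definition close the gap?** It may. Hypothyroidism treated with hormone replacement and immune rash treated with steroids fit its words. Section 6.2.2 also says that signs or symptoms of hepatitis and endocrinopathy are to be taken as immune-related when no other cause is found. But the same section of 14.0 then prints a study list with explicit cut-offs, and myocarditis is an example inside the Grade 2 cut-off. A site can defend either reading for a Grade 1 case.

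**Step 4: Part 3.** Appendix C narrows toxicity collection to AESIs and SAEs. Section 14.5 requires all AEs for the duration of study treatment and makes no exception for Part 3, nor does 14.0. The two instructions conflict. Part 3 follows Cycle 12, that is, after 12 × 3 = 36 weeks if no cycle is delayed, and runs until progression, so it holds the longest exposures.

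**Step 5: weight of one event.** With 20 to 25 subjects, and assuming all are treated and counted in the denominator, one subject missed for a given term lowers its incidence by 1/25 = 4 to 1/20 = 5 percentage points.

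**The case against.** The strongest reply is that the AESI list need not mirror the dosing rules: it defines what the sponsor wants to hear about quickly, whereas 6.2.2 governs treatment. The general definition is open-ended, and hepatitis is listed with no lower limit, the laboratory value being an addition to it. Some affected events, Grade 4 ones especially, would often be SAEs. All of that stands, and it limits the finding to ambiguity over non-serious cases.

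A reader might go further and infer any of the following. The documents do not support them.

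- *That these events are exempt from 24-hour reporting.* The general definition can bring them in. The cut-offs also have a purpose without being exclusions: Grade 2 can filter non-immune cardiac events, and 10 × ULN can act as a laboratory-only trigger.
- *That the sponsor has no other way to learn of them.* Section 5.6 provides for notifying the Study Physician, 14.0 directs questions about immune-related events promptly to the Medical Monitor, and 15.1 covers serious or unexpected events associated with study medication after discontinuation. The 5.6 route has no time limit, so it does not replace the 24-hour rule.
- *That non-serious events need not be recorded in Part 3.* Sections 14.5 and 14.0 say the opposite, and 5.6 requires the date of and reason for discontinuation in the eCRF. The Appendix C row is a conflict with those sections, not a waiver of them.

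**Conclusion.** The point holds as two inconsistencies to be reconciled. First, the named AESI list agrees neither with 6.2.2 nor fully with the general definition in 14.0. Grade 1 myocarditis and the transaminase range in Step 1 are permanent-discontinuation events that meet no listed item; hypothyroidism and rash are acted on but not named. The result is an unclear 24-hour duty for non-serious cases. Second, Appendix C and 14.5 give different instructions for Part 3, and sites that follow the schedule could lose non-serious events from the longest-exposure part of the primary safety result.

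The documents give no expected frequency for these events, so the number of reports or records affected cannot be estimated. The conclusion assumes that some sites will work from the printed list and the schedule table rather than from the general paragraphs. No view is taken on which clinical threshold is right. This is worth correcting in an amendment because safety is the primary objective and the change is small; it does not undermine the design.

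**What to change.** Four edits, all to reporting and recording:

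1. State in 14.0 that any event leading to permanent discontinuation of a study drug under 6.2.2 is reported as an AESI, whatever its grade or laboratory value.
2. Name hypothyroidism and immune-related skin events in the study list.
3. Reconcile the cardiac and hepatitis items with 6.2.2.
4. Reconcile the Appendix C toxicity row with 14.5, so that all AEs are collected in Part 3.

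The rule should not be extended to every hold criterion. That would bring in Grade 3–4 infection and isolated enzyme changes. Section 5.4 also admits subjects with liver metastases at AST or ALT up to 5 × ULN, so some would be above the 3 × ULN hold value at entry. Taking that limit to apply to both enzymes, none would be above the 5 × ULN discontinuation value at entry, so the narrower rule avoids the problem.

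The cost is a sentence, list edits and one table row in an amendment, plus some additional 24-hour reports and fuller AE entry in Part 3. No dose, hold or discontinuation rule changes.

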14.1 Attribution of Causality

The relationship of each event will be assessed by the Treating Physician and recorded on the CRF.

14.2 Atezolizumab Infusion Reactions

Severe infusion reactions have occurred in patients in clinical trials of atezolizumab. Infusion related reactions occurred in 1.3% (25/1978) of patients across clinical trials, 1.7% (9/523) of patients with urothelial carcinoma, and 1.6% (16/1027) of patients with NSCLC. Interrupt or slow the rate of infusion in patients with mild or moderate infusion reactions. Permanently discontinue atezolizumab in patients with Grade 3 or 4 infusion reactions.

14.3 Risks Associated with Atezolizumab

Refer to the Atezolizumab Investigator's Brochure for a detailed description of anticipated safety risks for atezolizumab.

Systemic immune activation is a rare condition characterized by an excessive immune response. Given the mechanism of action of atezolizumab, systemic immune activation is considered a potential risk when given in combination with other immunomodulating agents. Systemic immune activation should be included in the differential diagnosis for patients who, in the absence of an alternative etiology, develop a sepsis-like syndrome after administration of atezolizumab, and the initial evaluation should include the following:

- CBC with peripheral smear
- PT, PTT, fibrinogen, and D-dimer
- Ferritin
- Triglycerides
- AST, ALT, and total bilirubin
- LDH
- Complete neurologic and abdominal examination (assess for hepatosplenomegaly)

If systemic immune activation is still suspected after the initial evaluation, contact the Medical Monitor for additional recommendations.

14.4 Vigil Expected Side Effects

Vigil immunotherapy have been previously administered to patients with cancer. Side effects were minimal, the most frequent of which included local reactions at the site of injection. Potential adverse events are listed below.

Local skin reactions at the site of injection:

Erythema, tenderness, induration, urticaria/rash, pruritus.

Other expected adverse events:

Fever, myalgias/arthralgias, chills/rigors, nausea, fatigue, headache, thrombocytopenia and other cytopenias, hyperglycemia, vomiting, hypotension, infection at the immunization site.

In addition, there may also be a risk of autoimmune disease development, although to date no evidence of this has been seen in any vaccination study. There may also be worsening of tumor related symptoms secondary to immune related attack on subject's tumor.

